6.4.3.2 Safety analysis set

The safety analysis set will include all volunteers who receive at least one dose of study medication.

6.4.4 Methods of statistical analyses

The aim of this analysis is to determine the absolute bioavailability of AZD6140 following oral and intravenous administration.

The primary variables will be AUC (oral), AUC (IV), (Dose (IV) and Dose(oral) which are used in the calculation of Primary Endpoint F (Absolute bioavailability), where $F = (AUC(oral)/AUC(IV)) * (Dose(IV)/Dose(oral))$.

The primary contrast will be AZD6140(90 mg oral dose) vs. AZD6140(15 mg intravenous infusion).

Unless otherwise specified, descriptive statistics will include N, mean, standard deviation, minimum, median, and maximum.

A comprehensive statistical analysis plan will be prepared and finalized prior to database lock.

6.4.4.1 Pharmacokinetics

Only data from volunteers in the PK analysis set will be summarized and formally analyzed. All PK and plasma concentration data will be listed. Any data excluded from the analysis will be flagged accordingly.

The absolute bioavailability (F), where $F = (AUC(oral)/Dose(oral))/(AUC(IV)/Dose(IV))$, of AZD6140 following oral and intravenous administration will be analyzed as follows: Dose-normalized AUC values for the two formulations of AZD6140 will logarithmically transformed. An ANOVA model will then be fit using these log-scale values. The effect of formulation will be the primary contrast [$\log(AUC(oral)/Dose(oral)) - \log(AUC(IV)/Dose(IV))$]. The effect of formulation will be estimated using the $1s_{mean}$ and its 95% confidence interval. The $1s_{mean}$ and 95% confidence interval will then be exponentiated in order to estimate the absolute bioavailability. The $1s_{means}$ and 95% confidence intervals will also be calculated and exponentiated for each treatment formulation

PK parameters and plasma concentration data for each moiety (AZD6140, AR-C124910XX) will be summarized using descriptive statistics by AZD6140 formulation. Descriptive statistics will also include geometric mean and CV for all parameters except t_{max} , which will be summarized using only N, minimum, median and maximum. Geometric mean and individual plasma concentration-time profiles will be presented by AZD6140 formulation. AUC and C_{max} for each moiety will also be presented graphically as a function of AZD6140 formulation.

6.4.4.2 Safety

Only data from volunteers in the safety analysis set will be summarized and formally analyzed. Any data excluded from the analysis will be flagged accordingly.

Adverse events will be analyzed using frequency distribution by formulation. Clinical laboratory results, vitals signs and ECGs will be analyzed by formulation and protocol time point.

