The duration of healthy volunteer participation will be approximately 53 days, including:

- **Screening period (visit 1):** within 28 days before Study Period 1, Day 1.
- **Study Period 1 (visit 2):** will consist of admission to the clinical research centre on Day -1, administration of study medication according to randomisation schedule at Day 1, and continued inpatient stay until after the 72 hour post-dose blood collection is performed and all safety assessments are complete.
- **Washout Period:** at least 7 days between discharge from Study Period 1 and dosing of Study Period 2.
- **Study Period 2 (visit 3):** will consist of admission to the clinical research centre on Day -1, administration of study medication according to randomisation schedule at Day 1, and continued inpatient stay until after the 72 hour post-dose blood collection is performed and all safety assessments are complete.
- **Follow-up visit (visit 4):** within 3-5 days of the last inpatient day of Study Period 2.

Variables

- Pharmacokinetic

Treatment A (Oral administration): Blood samples for the pharmacokinetic assessment of AZD6140 and its metabolite AR-C124910XX will be obtained starting on Day 1 of Study Period 1 and Study Period 2 at the following time points:

- Pre-dose, 15min, 30min, 1, 1.5, 2, 2.5, 3, 4, 5, 6, 8, 10, 12, 16, 20, 24, 36, 48, and 72 hours post-dose.

Treatment B (Intravenous administration): Blood samples for the pharmacokinetic assessment of AZD6140 and its metabolite AR-C124910XX will be obtained starting on Day 1 of Study Period 1 and Study Period 2 at the following time points:

- Pre-dose, 15min, 30min, 40min, 50min, 1, 1.25, 1.5, 1.75, 2, 2.5, 3, 4, 5, 6, 8, 10, 12, 16, 20, 24, 36, 48, and 72 hours post dose.

Pharmacokinetics will be assessed by: absolute bioavailability (F), single dose C_{max} , t_{max} , AUMC, $AUC_{(0-t)}$, AUC, and $t_{1/2}$ of AZD6140 and AR-C124910XX, metabolite to parent C_{max} and AUC ratios, CL (IV only), CL/F (oral), V_z and V_{ss} (IV only), MAT (oral), and MRT of AZD6140 only.

- **Pharmacodynamic**

Not applicable.

- **Safety**

Safety and tolerability will be assessed by the incidence and severity of adverse events, vital signs, clinical laboratory parameters, physical examination, and electrocardiograms.

- **Genetics**

Genetic analysis of the genes that are involved in the absorption and disposition, and the response to AZD6140 including adverse effects may be performed.

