Urine alcohol/drugs of abuse screen ^g	X	X						X					
Randomisation			X										
AZD6140 PK Samples ^h			X	X	X	X			X	X	X	X	
AZD6140 Dose			X						X				
Concomitant Medication	X=====X												
AE Monitoring ⁱ	X=====X												
Genetic Informed Consent	X												
Genetic Blood Sample ^j			X										

	Screening Visit 1	Study Period 1 Visit 2					WASHOUT (At least 7 days)	Study Period 2 Visit 3					Follow-up Visit 4 (3-5 days after Study Period 2)
Day	-28 to -2	-1	1	2	3	4		-1	1	2	3	4	7 to 9
Assessment													
Confinement to Unit		X	X	X	X	X		X	X	X	X	X	

^a Includes height and weight; performed at screening only.

^b Brief physical exam pre-dose and 24 hours after dosing.

^c Vital signs include blood pressure and pulse and will be collected in the morning of Day 1 (pre-dose) and 2 and 4 hrs post IV dose.

^d Laboratory testing includes clinical chemistry, haematology and urinalysis parameters as specified in Section 4.4.1 and will be collected at screening, follow-up, Day -1 and at 24 hrs post dose.

^e Includes Hepatitis B, Hepatitis C, and HIV screens.

^f For female volunteers only; serum pregnancy test performed at screening, at Day -1 (Study Periods 1 and 2) and follow-up.

^g Urine alcohol and drugs of abuse screen to be performed at screening and on Day -1 (Study Periods 1 and 2).

^h Refer to Table 2 for sampling schedule. For IV dose, blood must be taken from arm contralateral to arm with infusion line.

ⁱ SAEs will be collected from the time of obtaining informed consent through the Follow-up Visit. All other AEs will be collected from the time of the first dose on Day 1 (Study Period 1) through the Follow-up Visit.

^j Performed pre-dose on Day 1 (Study Period 1).

Table 2 Pharmacokinetic Sampling Schedule (Study Periods 1 and 2)

AZD6140/AR-C124910XX Plasma Sampling		
Study Day	Treatment A (Oral administration)	Treatment B (Intravenous administration)
1	Pre-dose, 15min, 30min, 1hr, 1.5hr, 2hr, 2.5hr, 3hr, 4hr, 5hr, 6hr, 8hr, 10hr, 12hr, 16hr, and 20 hours post-dose	Pre-dose, 15min, 30min ^a , 40min, 50min, 1hr, 1.25hr, 1.5hr, 1.75hr, 2hr, 2.5hr, 3hr, 4hr, 5hr, 6hr, 8hr, 10hr, 12hr, 16hr, and 20 hours post-dose
2	24 hours post dose	24 hours post-dose
3	36 and 48 hours post-dose	36 and 48 hours post dose
4	72 hours post-dose	72 hours post-dose

^a Pharmacokinetic sample to be taken just prior to the end of the 30-minute infusion.

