3.2.2 Risk/benefit and ethical assessment

This study will not provide any direct medical benefits to the volunteer who participates. The benefit derived from this study will allow further understanding of the pharmacokinetic properties of AZD6140, which may be of benefit to further development of the drug and patients with ACS who may potentially receive AZD6140 in the future. Volunteers will be monitored under supervision in a clinical pharmacology unit (CPU), where management of any adverse events can take place.

The pre-clinical work in rats and marmosets indicates that AZD6140 exposure via the IV route in humans should be in the range or lower than that observed in animal studies following oral dosing, both on a C_{max} and AUC basis. The exposures in preclinical species have been determined in single dose studies as well as in studies up to 6 months in duration in rats and 12 months in duration in marmosets. The toxicities seen at the higher doses used in those studies support the safety of single 15 mg IV dosing in humans. There were no safety signals of concern in those species following IV administration of AZD6140, including perivenous irritation and flocculation.

The Investigator's Brochure for AZD6140 contains the information supporting the overall risk/benefit assessment of the test product and is available as a reference. It contains a summary of all relevant pharmaceutical, non-clinical and clinical findings with AZD6140.

Risks observed after administration of AZD6140 to healthy volunteers in Phase 1 studies are outlined below.

Phase 1 experience: The most common adverse events with an incidence of at least 2% reported to date in the Phase 1 studies with at least 3 days of AZD6140 dosing include: headache, somnolence, dizziness, epistaxis, nausea, abdominal pain, back pain, dyspnea, ecchymosis, lethargy, pharyngolaryngeal pain, blurred vision, postural dizziness, pollakiuria (frequent urination), and increased tendency to bruise. Other adverse events reported less frequently include: elevations in liver enzymes, tachycardia, orthostatic hypotension, rash, and gingival bleeding as possible adverse events associated with AZD6140 administration.

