3.4.2 Doses and treatment regimens

Each healthy volunteer will receive all of the following treatment regimens according to the randomised dose sequence.

Each volunteer will receive one of the following 2 treatments in the morning of Day 1 of each treatment period. The treatment periods will be separated by at least 7 days.

Each volunteer will receive:

- **Treatment A:** single 90 mg oral dose of AZD6140. (The tablet is not to be divided, chewed or crushed).
- **Treatment B:** 15 mg AZD6140 intravenous infusion - 150mL of AZD6140 solution for infusion, 0.1mg/mL as a 30-minute infusion with an infusion rate 300mL/hr.

The volunteers will receive the study medication following an overnight (10 hour) fast and will continue to fast for 4 hours post dose.

Water permitted ad libitum (freely) up until two hours prior to and not again until two hours after dosing. Meals will be provided on a fixed schedule.

Oral Dose

The oral dose will be administered with 240mL of room temperature water while the volunteer is sitting in an upright or in a semi-recumbent position. Volunteers must remain either sitting or semi-recumbent for at least 2 hours after dose intake.

IV Dose

The IV dose will be a single dose of 15 mg AZD6140 given as AZD6140 solution for infusion at a concentration of 0.1mg/mL. 150 mL solution will be infused as a 30-minute infusion at an infusion rate of 300 mL/hour. The solution will be dispensed from the supplied vials into an empty IV infusion bag.

Each supplied vial will have a volume of 50ml. A sufficient volume of additional AZD6140 solution will be added to the infusion bag in order to match to required volume to prime the IV tubings. Additional vials of AZD6140 solution will be supplied for use in priming.

The solution will be allowed to reach room temperature and be visibly checked for clarity and any precipitates prior to starting the infusion. The intravenous catheter should be flushed with saline before beginning the infusion. The drug will be administered using a calibrated infusion pump (IVAC 7100 Gold series pump). The pump and IV tubing will be primed with AZD6140 solution before infusion.

The first volunteer to receive the IV treatment will be given the infusion and observed for at least 30 minutes after the infusion has ended. If no adverse clinical reactions are observed after the first infusion completes, the remainder of volunteers may be dosed per unit routine.

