4.7.1.2 Recording of adverse events

Adverse events will be collected from the point of dosing (Study Period 1, Day 1) through completion of the follow-up visit (visit 4). Serious adverse events will be collected from

the time the informed consent is signed at screening (visit 1) through completion of the follow-up visit (visit 4).

The volunteer will be told to report any AE occurring during the study to the investigator or his personnel. Open standardized AE questioning, such as “Have you had any health problems since the previous visit?” will be done by the investigators or their personnel at each contact with the volunteer. The AE open standardized questioning should be done discreetly in order to prevent the volunteer from influencing each other.

Any AEs observed or reported by a volunteer and/or staff, will be recorded in the CRF. Any AE including clinical findings not resolved at the follow-up visit, will be followed up at an additional visit or telephone contact within 7 days after the follow-up visit or until resolved or explained.

Laboratory and vital sign abnormalities will not be recorded as an AE unless any criterion for an SAE is fulfilled, the volunteer discontinues the study due to the result(s), or the investigator insists that it should be reported as an AE. If a laboratory value or vital sign is associated with clinical signs and symptoms, the signs and symptoms should be reported as an AE and the associated laboratory or vital signs should be considered additional information. Any sign or symptom that fulfils the SAE definition (Appendix B) or is the reason for discontinuation of treatment of investigational products should be reported accordingly.

The following variables will be recorded for each AE noted:

- Onset, resolution
- Intensity (mild/moderate/severe)
- Action(s) taken
- Outcome of the AE
- Causality of the AE (yes or no)
- Whether it constitutes an SAE or not

The intensity rating is defined as:

1. Mild (awareness of sign or symptom, but easily tolerated)
2. Moderate (discomfort sufficient to cause interference with normal activities)
3. Severe (incapacitating, with inability to perform normal activities)

It is important to distinguish between serious and severe AEs. Severity is a measure of intensity whereas seriousness is defined by the criteria in Section 4.7.1.1. An AE of severe

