6.4.2.2 Secondary objectives

Characterization of the pharmacokinetics of AZD6140 following oral and intravenous administration of AZD6140 will be based on single dose C_{max} , t_{max} , $AUC_{(0-t)}$, AUC, $t_{1/2}$, and CL/F of AZD6140.

Characterization of the pharmacokinetics of AR-C124910XX following oral and intravenous administration of AZD6140 will be based on single dose C_{max} , t_{max} , $AUC_{(0-t)}$, AUC, $t_{1/2}$ of AR-C124910XX; and AR-C124910XX:AZD6140 C_{max} and AUC ratios.

Characterization of the pharmacokinetics of AZD6140 and AR-C124910XX after oral administration of AZD6140 will be based on single dose AUMC, MRT oral and MAT and CL/F for AZD6140.

Characterization of the pharmacokinetics of AZD6140 and AR-C124910XX after intravenous administration of AZD6140 will be based on single dose AUMC, MRT (IV) and CL, V_{ss} , and V_z for AZD6140. The safety and tolerability of AZD6140 will be examined by collection of adverse events, vital signs, and clinical laboratories.

The examination of the safety and tolerability of AZD6140 will be conducted based on AE, clinical lab, vital sign and ECG data.

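### Day 1 post-dose vital signs are scheduled only after the IV dose, so the plan cannot describe any post-dose vital-sign change after the 90 mg oral dose

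*Protocol*

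**What the plan says.** Vital signs are part of the safety objective. The synopsis states: "Safety and tolerability will be assessed by the incidence and severity of adverse events, vital signs, clinical laboratory parameters, physical examination, and electrocardiograms". Section 6.4.2.2 says much the same: "The examination of the safety and tolerability of AZD6140 will be conducted based on AE, clinical lab, vital sign and ECG data". Section 6.4.4.2 then fixes the summary: "Clinical laboratory results, vitals signs and ECGs will be analyzed by formulation and protocol time point".

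Table 1 in section 3.1 marks vital signs at screening, on Day -1 and Day 1 of each study period, and at follow-up. The row is empty for Days 2 to 4 of both periods. Footnote c explains the Day 1 entries: blood pressure and pulse "will be collected in the morning of Day 1 (pre-dose) and 2 and 4 hrs post IV dose". Section 4.4.3.1 adds the posture (sitting for 5 minutes) but no times, and refers back to Table 1.

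**The concern.** The analysis is set out by formulation and time point, but the schedule supplies post-dose time points for one formulation only. In the oral period the last scheduled reading before discharge is the pre-dose one on Day 1. A summary of post-dose vital signs, or of change from pre-dose, can be filled for the infusion and not for the tablet.

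Adverse event reporting does not close this gap. Section 4.7.1.2 says: "Laboratory and vital sign abnormalities will not be recorded as an AE unless any criterion for an SAE is fulfilled". The other two exceptions are discontinuation because of the result and the investigator's insistence; associated symptoms are reported as events. A symptom-free change in pulse or pressure after the oral dose would thus be neither scheduled for measurement nor normally recorded.

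The measurement is relevant to this drug. Section 3.2.2 lists "tachycardia, orthostatic hypotension, rash, and gingival bleeding as possible adverse events associated with AZD6140 administration". A sitting pulse bears on tachycardia. Sitting readings do not test orthostatic hypotension, so nothing is claimed for that event.

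**Working it through.** The plan states no count of vital-sign readings, so there is no figure to reproduce. The check is a count from Table 1 and footnote c, where one reading means one set of blood pressure and pulse.

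**Inputs**
- Volunteers: up to 12 randomised, 10 evaluable (synopsis; section 3.1).
- Each volunteer receives both treatments, so each completer has one oral and one IV dosing day (section 3.4.2).
- Vital-sign days: screening, Day -1 and Day 1 of each period, follow-up (Table 1).
- Day 1 times: pre-dose in both periods, then 2 h and 4 h after the IV dose (footnote c).

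**Readings per completer as scheduled**

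Screening 1 + Day -1 in two periods 2 + Day 1 pre-dose in two periods 2 + post-IV 2 + follow-up 1 = 8. For 12 completers, 8 × 12 = 96.

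**In-period readings by treatment**

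| | Oral period | IV period |
|---|---|---|
| Day -1, 12 completers | 12 | 12 |
| Day 1 pre-dose, 12 completers | 12 | 12 |
| Post-dose before discharge, 12 completers | 12 × 0 = 0 | 12 × 2 = 24 |
| Post-dose before discharge, 10 completers | 10 × 0 = 0 | 10 × 2 = 20 |

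**Could another assessment supply the oral readings?**
- The brief physical examination at 24 h covers abdomen, lungs and cardiovascular system (section 4.4.4.3). Blood pressure and pulse are not listed.
- In sequence BA, the next scheduled vital signs after the oral dose are at follow-up. Table 1 places this on Days 7 to 9, which is 6 to 8 days after dosing, or 144 to 192 h.
- In sequence AB, they are on Day -1 of Period 2. The synopsis puts at least 7 days between discharge (Day 4) and Period 2 dosing, so dosing is on Day 11 or later and Day -1 on Day 10 or later: at least 9 days, or 216 h, after the oral dose.
- Section 1.1 gives a parent half-life of about 11 h and says that the active metabolite runs roughly parallel. Even the earliest of these readings is 144 / 11 = 13.1 half-lives after dosing, so none describes the vital signs during exposure to the tablet.

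**With the 2 h and 4 h readings after both doses**

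8 + 2 = 10 per completer, and 10 × 12 = 120 in all. Post-dose readings become 24 oral and 24 IV with 12 completers (20 and 20 with 10).

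**The case against.** The best reply is that the restriction to IV is deliberate. Footnotes b and d of the same table give post-dose times without naming a route; only footnote c names one. The IV route is the less tested: its dose was set from marmoset bioavailability (section 3.2.1), its safety support in section 3.2.2 is animal work, and section 3.4.2 adds an observation step for the first infusion. Oral dosing already has Phase 1 experience, including a single 1260 mg dose (section 1.1). This is plausible, but no section gives it as the reason for the vital-sign times, and it would not change what the oral data can show.

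A second reply is that section 6.4.4.2 can be carried out as it stands, by summarising each formulation at the times set for it. PK times also differ by route, and the objective is to examine safety, not to compare routes. This is fair: the text promises no oral-versus-IV contrast of vital signs. It remains true that the safety of the oral dose is to be judged partly on vital signs, and that none is scheduled while the tablet is acting.

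A third reply is that volunteers are watched. Section 3.3.4 refers to constant monitoring in the unit for 72 hours, and section 3.2.2 to supervision in a clinical pharmacology unit. A reader might infer from the gap that volunteers go unobserved after the oral dose; the documents do not support that. But monitoring without stated times provides no scheduled readings to summarise.

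**Conclusion.** The point holds in a limited form. The schedule yields 0 post-dose vital-sign readings in the oral period against 24 in the IV period with 12 completers (0 against 20 with 10). Vital signs after the 90 mg oral dose therefore cannot be described at any time between dosing and discharge. The count assumes that all completers receive both treatments and that only scheduled readings enter the summary. Unscheduled or unit-routine readings may exist, but the protocol sets no times for them.

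The consequence is confined to descriptive data for a secondary objective. The primary bioavailability analysis, adverse event collection, 24 h laboratory tests and 24 h brief examinations are untouched.

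Two stronger readings are not supported. A reader might infer that the oral period has no vital signs at all, or that half of the vital-sign assessment is lost. The oral period does have Day -1 and Day 1 pre-dose readings, and only the post-dose readings are absent. A reader might also argue that the oral dose matters more because it is 90 / 15 = 6 times the IV dose. The resulting exposure ratio depends on the bioavailability, which section 1.2 says is unknown, and total exposure says little about effects at 2 to 4 h.

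**What to change.** Delete the word IV from footnote c to Table 1, so that vital signs are taken pre-dose and at 2 h and 4 h after either dose. Sections 6.4.2.2 and 6.4.4.2 need no change. This has to be done before dosing starts. If the sponsor confirms that readings after IV only were intended, footnote c should say so and section 6.4.4.2 should limit its post-dose vital-sign summary to the infusion.

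The cost is two extra sitting blood-pressure and pulse readings per volunteer, 2 × 12 = 24 in total, while volunteers are already confined. Posture is little obstacle at 2 h, since after the oral dose "Volunteers must remain either sitting or semi-recumbent for at least 2 hours after dose intake". Volunteers also "will continue to fast for 4 hours post dose", so the 4 h reading can be taken before the first meal. PK samples are due at 2 h and 4 h and have priority under section 4. The same section lets safety assessments be made up to 15 minutes before the time point, which leaves room for 5 minutes of sitting and the reading without delaying the sample.
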